- After completing the surveys, the participant will take test product. The participant will take 2 capsules with 6-8 oz. of water per headache episode. With a max of 6 pills per day. (If participant takes 6 pills in 1 day this will be defined as 3 headache episodes and the patient will be exited from the study).
- After taking the test product, the participant will complete a Mankoski pain scale at 15 minutes, 30 minutes, and 1 hour after taking the test product.
- Once the participant's symptoms resolve, the participant will complete the headache diary.
- If the participant takes any other medication outside of the test product, the participant will record this on the headache diary.
- After taking the test product, the participant will be instructed to fill out an Adverse Event form for any side-effects experienced.
- After the first headache episode, the participant will be asked to complete the same process for another 2 headache episodes; however, these are not required.
- If the participant completes the required assessments for a total of 3 headache episodes, they will be prompted, by email, to exit the study.

- If the participant only completes the required assessments for the required 1 headache episode, the participant will be prompted, by email, to complete the study exit form and will be exited from the study on day 60 (60 days from the day of receipt of the test product).
- The sponsor nor Hawthorne Effect Inc. will not make any attempt to collect any unused product.
- Upon receipt of study exit survey and review of completed study forms, participant will receive an Amazon gift card of \$25 via email.

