6.2 Study Schedule of activities

Assessments	Screening	Consent	Before Receipt of Test Product	Product Received	Event 1	15 Minutes After Event Start	30 Minutes After Event Start	60 Minutes After Event Start
Study Window								
Screening Survey	Х							
Consent		X						
Baseline Survey			Х					
Demographics			Х					
Medications & Supplements			Х					
Acknowledgement of receipt of test product				X				
Headache Diary					X			X
10-point Mankoski Scale					Х	Х	Х	Х
Test Product Consumed					Х			
AE Assessment					X	X	X	X
Study Exit Survey								

Assessments	Event 2	15 Minutes After Event Start	30 Minutes After Event Start	60 Minutes After Event Start	Event 3	15 Minutes After Event Start	30 Minutes After Event Start	60 Minutes After Event Start	Study Exit
Study Window									
Screening Survey									
Consent									
Baseline Survey									
Demographics									
Medications & Supplements									
Acknowledgement of receipt of test product									
Headache Diary	Х			X	Х			X	
10-point Mankoski Scale	X	X	Х	X	X	X	X	X	
Test Product Consumed	Х				X				
AE Assessment	Х	X	Х	X	X	X	Х	X	Х
Study Exit Survey									X

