6.4 Adverse Event and Safety Monitoring

Adverse Events (AEs) are defined as any untoward medical occurrences described by the study participant. All AEs will be self-reported and documented on the platform. The AEs will be reviewed by the study team including the remote trial coordinator and study principal investigator and reported according to the IRB requirements. Participants who experience adverse events will be advised to stop taking the test product and seek medical attention.

In the event that a participant experiences an adverse event, the clinical study manager or clinical ops coordinator will notify both the PI and Sponsor. The Sponsor will take appropriate action according to their standard operating procedures for any adverse events that warrant action by the Sponsor.

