6.4.2 Adverse Event Relationship

Each reported AE will be assessed by the Investigator for relatedness, severity and causality.

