- **3** Annoying enough to be distracting. Mild painkillers take care of it (Aspirin, Ibuprofen).
- **4** Can be ignored if you are really involved in your work, but still distracting. Mild painkillers remove pain for 3-4 hours.
- **5** Can't be ignored for more than 30 minutes. Mild painkillers ameliorate pain for 3-4 hours.
- **6** Can't be ignored for any length of time, but you can still go to work and participate in social activities. Stronger painkillers (Codeine, narcotics) reduce pain for 3-4 hours.
- **7** Makes it difficult to concentrate, interferes with sleep. You can still function with effort. Stronger painkillers are only partially effective.
- **8** Physical activity severely limited. You can read and converse with effort. Nausea and dizziness set in as factors of pain.
- 9 Unable to speak. Crying out or moaning uncontrollably near delirium.
- 10 Unconscious. Pain makes you pass out.

	Afte	r your	headache	resolved	please com	plete any	of the	following	questions i	if applicabl
--	------	--------	----------	----------	------------	-----------	--------	-----------	-------------	--------------

Did your symptoms resolve completely with the test product? Yes No If yes, time of complete symptom resolution:						
Did you need to take another medication: Yes No						
Medication #1:	Dose:	Time:				
Medication #2:	Dose:	Time:				
Medication #3:	Dose:	Time:				
Did your symptoms resolve completely with taking your medication? Yes No						
After taking medication, time of complete resolution of symptoms:						
Did you experience any side effects after taking the test product? (Y/N) If yes, Please fill out the Adverse Event form.						

13.1.6Appendix F Study Exit Form

symptoms? (y/n)

Study Exit

1.	Pleas	e rate y	our ov	erall ex	perience w	ith th	e test	produc	t.	
0 Poor	1	2	3	4	5 Neutral	6	7	8	9	10 Excellent
1a	. Why?	(free r	espons	e)						
2.	Do yo	ou feel t	hat th	e test p	roduct help	ed w	ith yo	ur head	aches i)
0 Not at	all	2	3	4	5 Neutral	6	7	8	9	10 definitely
3. How likely are you to recommend the test product to your friends or family members?										
0 Not Li	1 kely	2	3	4	5 Neutral	6	7	8	9	10 Extremely Likely
4. Do you feel that the test product helped your body cope with occasional tension and occasional head discomfort?										
0 Not at	all	2	3	4	5 Neutral	6	7	8	9	10 definitely
5.		=	_		you like to sistency, or				-	xperience with the sponse)

6. Did the test product help prevent you from having to take any other medication for your

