
13.1.7Appendix G Adverse Event Form

Tension AE document

- 1. Did you experience any side effects after taking the test product? Y/N
 - a. If so, did you experience any of the following
 - o itching, rash, hives, throat/lip/tongue swelling, wheezing
 - low blood pressure, fainting, chest pain, shortness of breath, palpitations, irregular heart beat
 - o severe, persistent nausea, vomiting, diarrhea, or abdominal pain
 - o difficulty urinating, decreased urination
 - o fatigue, appetite loss, yellowing skin/eyes, itching, dark urine
 - severe joint/muscle pain
 - o slurred speech, one-sided weakness of face, arm, leg, vision
 - o abnormal bleeding from nose or gums
 - o blood in urine, stool, vomit,
 - o marked mood, cognitive, or behavioral changes, thoughts of suicide
 - o Other:
- 2. Please give a description of the event
- 3. How soon after taking the test product did you experience the side effect?
- 4. What did you do to alleviate the side effect?
- 5. Did you have to go to the hospital or see a doctor for this side effect?
 - a. Please describe any diagnosis or treatment that they provided.
 - b. If you were seen in the hospital, please upload any discharge paperwork or other documents from the hospital.

13.1.8Appendix H Test Product Insert

Welcome to the Tension Headache Relief Trial!

We appreciate you taking the time to participate in this trial. As you may already know, the aim of this study is to measure the impact the test product has on your headache symptoms. Please take the time to read the following information below to become acquainted with the trial instructions.

Instructions upon Study Product Receipt:

- 1. Please log onto the study portal and acknowledge the receipt by completing the 'Start Form'
- 2. Enclosed in the study bag, please find a 3-episode supply of the tension relief test product.
- 3. You will take the test product the next time you have a headache and need to take something to relieve the discomfort.

Instructions Once Product Intake Begins:

- 1. The next time you have a headache and feel the need to take the test product, you will FIRST start the headache diary (paper forms included in this package).
 - You will complete the date of the episode, the time the episode began, what triggered the headache, type/description of the pain, its location, and record other symptoms (if applicable).
 - REMINDER: DO NOT TAKE ANY OTHER MEDICATION/SUPPLEMENT DURING THE HOUR AFTER TAKE THE TEST PRODUCT.

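### Adverse events are defined without regard to cause, but the forms ask only about side effects, so events a participant blames on something else may never reach the investigator

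*Combined protocol and SAP*

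**What the plan says.** Section 6.4 sets the definition: "Adverse Events (AEs) are defined as any untoward medical occurrences described by the study participant". It needs no causal link to the product. The same section fixes the data source: "All AEs will be self-reported and documented on the platform". Section 6.4.2 places the causal judgement elsewhere: "Each reported AE will be assessed by the Investigator for relatedness, severity and causality".

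The collection points use other words:

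- Section 6.1: "After taking the test product, the participant will be instructed to fill out an Adverse Event form for any side-effects experienced".
- Appendix E, among the items completed after the headache has resolved: "Did you experience any side effects after taking the test product? (Y/N) If yes, Please fill out the Adverse Event form".
- Appendix G, question 1: "Did you experience any side effects after taking the test product? Y/N". The symptom checklist follows under "If so, did you experience any of the following". Items 3 to 5 also refer to the side effect.

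The table in section 6.2 has a row "AE Assessment", marked at each headache event, at 15, 30 and 60 minutes after it, and at study exit. Appendix G is the only adverse event instrument shown. The synopsis and section 3 say, in their lists of secondary endpoints, that adverse events will be summarized.

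**The concern.** In everyday use a side effect is something the product caused. A participant who reads the question that way makes a causal judgement before the investigator sees anything, and a no ends the enquiry. The definition in 6.4 and the assessment in 6.4.2 would then apply only to events that the participant had already linked to the product.

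The protocol's own content makes this plausible. Nausea and headache are among the anticipated events in section 6.4.1, while level 8 of the pain scale in the diary describes nausea and dizziness as part of the pain. A participant with nausea could reasonably blame the headache. Other medicines are allowed after the one-hour report (section 4.2), so a later event could be blamed on one of those. The definition of a serious adverse event in 6.4.3 goes by outcome, not cause, yet a serious event thought unrelated has no worded prompt on the forms shown.

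At stake is the completeness of the safety summary. The study has one arm, no clinic visits and, by its own section on limitations, no medical review of symptoms, so little else would bring a missed event to light. The efficacy analysis is not affected.

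**Working it through.** The plan states no figure on this point, so the main check compares texts.

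| Step | Where | Scope of the wording | Depends on a yes? |
|---|---|---|---|
| Definition | 6.4 | Any untoward medical occurrence | No |
| Relatedness | 6.4.2 | Each reported event, judged by the investigator | Needs a report |
| Instruction to participants | 6.1 | Side effects, after taking the product | – |
| Diary | 6.1, Appendix E | Opens at headache onset, for every episode | No |
| Closing diary item | Appendix E | Side effects | A yes leads to the form |
| First question of the form | Appendix G | Side effects | – |
| Checklist | Appendix G | Broad, ends with an open category | Yes |
| Scheduled assessments | 6.2 | No wording given | – |
| Exit form | Appendix F | Product experience, benefit, recommendation, other medication avoided | No health-event item visible |

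Every collection point whose wording can be read uses the narrower term. The condition acts at two places only: between the diary and the form, and inside the form before the checklist.

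**Illustration of what under-reporting would do.** Let n be the number treated, p the true proportion with a given event, and c the share of those events that get reported. Participants are taken as independent, with at most one such event each.

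- n = 97, the desired number of treated participants in section 5.1.
- p and c are assumptions. The documents give no value for either, so a range is shown.

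Chance of at least one report = 1 − (1 − p × c)^97

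At p = 3%:

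- c = 100%: 1 − 0.97^97 = 0.948
- c = 50%: 1 − 0.985^97 = 0.769
- c = 25%: 1 − 0.9925^97 = 0.518

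| True p | c = 100% | c = 50% | c = 25% |
|---|---|---|---|
| 1% | 62.3% | 38.5% | 21.6% |
| 3% | 94.8% | 76.9% | 51.8% |
| 5% | 99.3% | 91.4% | 70.5% |

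The expected number of participants with a report is 97 × p × c. At p = 3% this is 2.9, 1.5 and 0.7. Expected reported incidence falls in direct proportion to c.

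**The case against.** The case for leaving the forms alone has several parts.

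- **The question is framed by time.** It asks what happened after the product was taken, and *side effect* is not defined for participants. Some will report anything that followed. This stands as a reason not to claim a known loss. It does not remove the term that may turn others away.
- **The form is broad once open.** The checklist covers cardiac, neurological, hepatic, bleeding and mood symptoms and has an open category, and item 2 asks neutrally about the event. This is true, but it helps only after a yes.
- **The definition itself rests on what participants describe.** One could say that an unreported event falls outside it. But the definition turns on description, not attribution, and the forms narrow what participants are asked to describe.
- **Health status at exit is planned for.** Sections 7.1 and 7.3 mention a general-health questionnaire at baseline and exit. No such item is visible on the exit form, although its free-text item 5 is partly illegible in the copy reviewed.
- **Some text could not be read.** The participant insert (Appendix H) breaks off partway, and the appendix listed as 13.1.9 was not available. Adverse event wording may stand there. The forms that can be read would still differ from 6.4.

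Stronger readings are tempting, and the documents do not support them. A reader might infer that the diary opens only when a side effect is reported; it opens at headache onset. A reader might infer that section 6.2 requires an adverse event question on the exit survey; the table lists the assessment and the survey as separate rows, both marked at exit. And a reader might treat adverse event incidence as a formally specified endpoint; the plan promises only a summary, and the endpoint list in 7.1 omits adverse events.

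**Conclusion.** The mismatch is real and rests on the text alone: the definition is neutral as to cause, and every readable prompt is not. Events that participants do not attribute to the product may fail to reach the investigator, and no other readable instrument would catch them.

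The size is unknown. A reader might conclude that events certainly are lost, or that the count is necessarily biased by some stated factor. The documents support neither, because they give no reporting rate and do not show how participants would understand the term. The fall from 95% to 77% or 52% at 3% incidence shows only what 50% or 25% reporting would do with 97 treated participants.

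This is a low-cost change worth making to improve safety capture. It is not a flaw in the primary analysis.

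**What to change.** 1. In the diary and in question 1 of Appendix G, replace the gate with a cause-neutral question, for example: *Have you had any new or worsening health problem since taking the test product, whether or not you think the product caused it?*
2. In items 3 to 5 of Appendix G, refer to the event instead of the side effect.
3. Align the instruction in section 6.1 with the definition in 6.4.
4. Use the same question for the assessment that section 6.2 already schedules at study exit, and name the instrument.
5. Check the rest of the participant insert and the remaining appendix for the same term.

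The checklist can stay under a yes. Showing it to everyone is a further option, but it could draw out symptoms of the headache itself, and the correction does not depend on it.

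The cost is rewording both the electronic forms and their paper copies, and more reports of unrelated events, headache symptoms among them, for the investigator to review. Section 6.4 attaches notification of the investigator and sponsor, and advice to the participant, to adverse events in general, so these would follow more reports too. The sponsor should confirm that this is what 6.4 intends.

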6.4.1 Anticipated Adverse Events

Anticipated Adverse Events are complications that are known to be associated with the test product (in high doses exceeding recommended use):

- Diarrhea
- Nausea
- Stomach Cramps
- Acid Reflux
- Skin Rashes
- GI Bleeding
- Headaches
- Liver Damage

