- 2 Minor Annoyance occasional strong twinges. No medication needed.
- **3** Annoying enough to be distracting. Mild painkillers take care of it (Aspirin, Ibuprofen).
- **4** Can be ignored if you are really involved in your work, but still distracting. Mild painkillers remove pain for 3-4 hours.
- **5** Can't be ignored for more than 30 minutes. Mild painkillers ameliorate pain for 3-4 hours.
- **6** Can't be ignored for any length of time, but you can still go to work and participate in social activities. Stronger painkillers (Codeine, narcotics) reduce pain for 3-4 hours.
- **7** Makes it difficult to concentrate, interferes with sleep. You can still function with effort. Stronger painkillers are only partially effective.
- **8** Physical activity severely limited. You can read and converse with effort. Nausea and dizziness set in as factors of pain.
- 9 Unable to speak. Crying out or moaning uncontrollably near delirium.
- 10 Unconscious. Pain makes you pass out.

Pain Scale at 30 minutes

Please rate your pain 30 minutes after taking the test product. Circle your answer.

- 0 Pain Free
- 1 Very minor annoyance occasional minor twinges. No medication needed.
- 2 Minor Annoyance occasional strong twinges. No medication needed.
- **3** Annoying enough to be distracting. Mild painkillers take care of it (Aspirin, Ibuprofen).
- **4** Can be ignored if you are really involved in your work, but still distracting. Mild painkillers remove pain for 3-4 hours.
- **5** Can't be ignored for more than 30 minutes. Mild painkillers ameliorate pain for 3-4 hours.
- **6** Can't be ignored for any length of time, but you can still go to work and participate in social activities. Stronger painkillers (Codeine, narcotics) reduce pain for 3-4 hours.
- **7** Makes it difficult to concentrate, interferes with sleep. You can still function with effort. Stronger painkillers are only partially effective.
- **8** Physical activity severely limited. You can read and converse with effort. Nausea and dizziness set in as factors of pain.
- 9 Unable to speak. Crying out or moaning uncontrollably near delirium.
- 10 Unconscious. Pain makes you pass out.

Pain Scale at 1 hour

Please rate your pain 1 hour after taking the test product. Circle your answer.

- 0 Pain Free
- 1 Very minor annoyance occasional minor twinges. No medication needed.
- 2 Minor Annoyance occasional strong twinges. No medication needed.

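### The adverse event form (Appendix G) asks neither severity nor duration, although section 6.4.2 requires a severity assessment, and it prompts no non-bleeding GI event in mild form

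*Combined protocol and SAP*

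**What the plan says.** Section 6.4.2 states: "Each reported AE will be assessed by the Investigator for relatedness, severity and causality". No grading scale accompanies it. Section 6.4 makes all adverse events self-reported, with review by the study team and the principal investigator. Section 3 lists a summary of adverse events among the secondary items, and section 7 plans no table by grade or duration.

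Appendix G opens with an unrestricted question: "Did you experience any side effects after taking the test product? Y/N". A checklist of ten named lines and a write-in line follows. The form then asks for a description, the time to onset ("How soon after taking the test product did you experience the side effect"), what was done to relieve the event, and whether a doctor or hospital was needed, with two sub-items on treatment and discharge papers. The GI line of the checklist is "severe, persistent nausea, vomiting, diarrhea, or abdominal pain".

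The diary in Appendix E repeats the open side-effect question after the headache has resolved and sends the participant to the form: "If yes, Please fill out the Adverse Event form". The schedule in section 6.2 has an "AE Assessment" row marked at each time point of each episode and at exit.

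Section 6.4.1 lists eight anticipated events: diarrhea, nausea, stomach cramps, acid reflux, skin rashes, GI bleeding, headaches and liver damage.

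**The concern.** Two features of the form sit badly with the rest of the protocol.

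First, a required assessment has no matching question. Participants are never seen in a clinic (section 4), and section 11 acknowledges that symptoms get no medical review. The investigator's severity judgement therefore depends on what the participant writes, and the form does not ask for the two facts that would most directly support a grade: how bad it was and how long it went on.

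Second, the checklist prompts the commonplace GI effects only above a threshold, and omits acid reflux. A participant with mild queasiness who reaches the checklist finds no line that fits.

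What is at stake is the tolerability description. Section 2.2.2 presents relief without the unwanted side effects of other remedies as a potential benefit, and section 10 foresees promotional use of the results. Mild GI effects bear directly on that message for a product containing salicin. As designed, they would arrive as ungraded free text.

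**Working it through.** The plan gives no figure to reproduce, and no power or effect-size formula applies. The check compares Appendix G with sections 6.4.1, 6.4.2 and 6.2.

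**1. What the form asks.** There are 5 numbered items plus sub-items 1a, 5a and 5b: 5 + 3 = 8 prompts.

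| Prompt | Severity grade? | Duration? |
|---|---|---|
| 1 Any side effect (yes/no) | no | no |
| 1a Checklist | no; some lines carry a threshold word | one line only, through its wording |
| 2 Description | only if volunteered | only if volunteered |
| 3 Time to onset | no | no |
| 4 Remedy used | indirect clue | no |
| 5 Doctor or hospital | indirect clue | no |
| 5a Diagnosis or treatment | indirect clue | no |
| 5b Discharge papers | indirect clue | no |

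Prompts asking for a grade: 0 of 8. Prompts asking for duration: 0 of 8.

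**2. Threshold words in the checklist.** Of the 10 named lines, 2 use *severe* (GI; joint and muscle pain) and 1 uses *marked* (mood and behavior). That leaves 10 − 2 − 1 = 7 with neither word.

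**3. Anticipated events against the checklist.**

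| Event in 6.4.1 | Line in Appendix G |
|---|---|
| Skin rashes | yes, no threshold |
| GI bleeding | yes, no threshold (blood in stool or vomit) |
| Liver damage | not named; a symptom line, no threshold |
| Nausea | only above the threshold |
| Diarrhea | only above the threshold |
| Stomach cramps | nearest term is abdominal pain, only above the threshold |
| Acid reflux | none |
| Headaches | none, but pain is rated before dosing and at 15, 30 and 60 minutes, the last prompt being "Please rate your pain 1 hour after taking the test product" |

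Total: 3 + 3 + 1 + 1 = 8. The non-bleeding GI events are nausea, diarrhea, stomach cramps and acid reflux. Lines that fit a mild case: 0 of 4.

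**4. Sensitivity to the reading.** Step 3 takes the two adjectives to cover the whole GI line, which is the natural reading. If they qualify nausea alone, diarrhea and abdominal pain are prompted in any form, and 2 of 4 events (nausea and acid reflux) lack a mild prompt.

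**5. Opportunities to report.** Section 6.2 schedules 3 episodes × 4 time points + 1 at exit = 13 assessments at most. These repeat the chance to report; nothing shown indicates that they add a severity or duration question. In the diary as printed, the side-effect question appears once per episode, after the four pain scales.

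**The case against.** The strongest reply is that the form already captures everything and that grading belongs to the investigator. Much of this stands.

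- **Capture.** The opening question is unrestricted, the diary repeats it, section 6.1 asks for the form after any side effect, and the write-in line and description accept any event. A participant with mild nausea who answers yes is counted. A reader might infer that mild GI events are lost or that the adverse event rate is biased downward. The documents do not support that: some under-prompting is possible, but its effect cannot be computed, and up to 13 scheduled assessments make it less likely.
- **Who grades.** Section 6.4.2 assigns severity to the investigator, not to the participant, and no section requires duration. The investigator's own assessment record is not among the documents. A reader might infer that the study has no severity field anywhere; this is shown only for the participant form. Remedy, care sought, discharge papers, coordinator prompts (section 6.3) and telephone contact (section 4) can all inform a grade. However, no query procedure for obtaining one is described.
- **Coding.** It is tempting to say that other anticipated events arrive as clean ticked terms while GI events arrive as free text. They do not. Rash shares its line with swelling and wheezing, blood in stool shares one with blood in urine, and liver damage is only a group of symptoms. If whole lines are ticked, coding needs the description for every event.
- **Ticks without a threshold word.** It would also be wrong to say that a tick on the other 7 lines says nothing about severity. Fainting, throat swelling and one-sided weakness are alarm symptoms in themselves.
- **Benchmark.** The checklist reads as an alarm-symptom screen, and nothing says it must mirror section 6.4.1, which ties its list to excess dosing: "Anticipated Adverse Events are complications that are known to be associated with the test product (in high doses exceeding recommended use". These events may be rare at study dose.

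What survives is narrow: the form does not ask for information that the required severity assessment needs, and it prompts ordinary GI effects only above a threshold.

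**Conclusion.** The point holds as a minor weakness in safety data collection. The participant form has 0 of 8 prompts on severity and 0 of 8 on duration, although section 6.4.2 requires severity to be assessed. None of the 4 anticipated non-bleeding GI events is prompted in mild form (2 of 4 lack a mild prompt on the narrower reading of the GI line). The count treats stomach cramps as the form's abdominal pain and takes section 6.4.1 as a reasonable, though not mandated, benchmark.

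The consequence is that grades will rest on inference from uneven material, and mild GI events will be harder to grade and tabulate consistently. The documents establish neither under-reporting of any given size nor an inability to meet section 6.4.2. The primary endpoint and the sample size are untouched.

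**What to change.** In Appendix G, on paper and in the portal:

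1. For each reported event, add *How severe was it? Mild / Moderate / Severe* and *How long did it last? (or still ongoing)*.
2. Drop the severity and persistence wording from the GI line and replace the bundle with separate tick boxes: nausea; vomiting; diarrhea; stomach cramps or abdominal pain; acid reflux. Separate boxes matter because a reworded bundle would still not identify the symptom.
3. Have the portal flag any event rated severe for priority review, so that the alarm function of the present GI line is kept.

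The investigator still assigns the final grade under section 6.4.2; the participant's answer is an input to it.

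The cost is a small edit to one form and slightly more burden for participants who report an event. More minor events will be recorded and reviewed, and some will be background symptoms that a one-arm study cannot attribute to or separate from the product. The safety summary should say so.
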